7.2 Adverse Events

AEs will be coded using the Medical Dictionary for Regulatory Activities (MedDRA) coding dictionary [REDACTED] preferred term (PT) and system organ classification (SOC).

An AE will be considered treatment emergent (TEAE) if it begins or worsens in severity after the first dose of the study drug through 30 days after the last dose of study drug, or the date of initiation of another investigational agent or surgical intervention.

Drug-related TEAEs are defined as definitely related, possibly related, or probably related to study drug. Any AEs with missing relationship to study drug will be considered as related to study drug.

All TEAEs with start dates prior to first dose date in Visit 4 EEC Treatment Session will be classified as AEs occurred in Visit 3 EEC Treatment Session.

An overall summary for number of subjects with events in each treatment will be provided including:

- Number of subjects with at least one TEAE
- Number of subjects with at least one Ocular TEAE
- Number of subjects with at least one drug-related TEAE
- Number of subjects with at least one drug-related Ocular TEAE
- Number of subjects with at least one serious TEAE
- Number of subjects with at least one serious Ocular TEAE
- Number of subjects with at least one TEAE leading to study discontinuation
- Number of subjects with at least one Ocular TEAE leading to study discontinuation

An AE is classified as an ocular AE if system organ class is coded as eye disorders.

The following types of summary for each treatment will be provided. Summaries will be sorted by decreasing frequency of PT within SOC which will be sorted alphabetically.

- TEAEs by SOC and PT
- Ocular TEAEs by SOC and PT
- Non-Ocular TEAEs by SOC and PT
- TEAEs by Casualty, SOC and PT

- Ocular TEAEs by Casualty, SOC and PT
- Non-Ocular TEAEs by Casualty, SOC and PT
- Serious TEAE by SOC and PT
- Ocular Serious TEAE by SOC and PT
- Non-Ocular Serious TEAE by SOC and PT
- TEAE by SOC, PT and maximum Severity
- Ocular TEAE by SOC, PT and maximum Severity
- Non-Ocular TEAE by SOC, PT and maximum Severity
- TEAEs leading to study discontinuation by SOC and PT
- Ocular TEAEs leading to study discontinuation by SOC and PT
- Non-Ocular TEAEs leading to study discontinuation by SOC and PT

If a preferred term or system organ class was reported more than once for a subject, the subject would only be counted once in the incidence for that preferred term or system organ class.

- In the tabulation of TEAE by severity, only the most severe PT or SOC for each subject will be included. Missing severity will be counted as Severe.
- In the summary of drug-related TEAEs, the strongest relationship will be included.

Listing will be provided including for Safety Population:

- All AEs
- Serious TEAEs
- TEAEs leading to study discontinuation

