### **7.6 Adverse Events**

AEs will be collected from the time the subject signs the informed consent form through 30 days after the last dose of IP. AEs must be recorded in the electronic CRF. The Sponsor and investigator or qualified site staff will review and evaluate AEs on an ongoing basis. See [Section 9](#) for further detail on AE reporting.

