### 9.1.2 Treatment-Emergent Adverse Events

A TEAE is defined as an AE that occurred during the clinical trial after the first dose of IP or was present prior to dosing, and exacerbates after the first dose of IP.

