### 9.1.3 Serious Adverse Events

An SAE is any AE that results in any of the following outcomes:

- death;
- a life-threatening AE;

Note: An AE is considered “life-threatening” if, in the view of either the investigator or Sponsor/designee, the subject is at immediate risk of death as a result of the AE. “Life threatening” does not include an AE that, had it occurred in a more severe form, might have caused death.

- inpatient hospitalization or prolongation of existing hospitalization;

Note: The term “inpatient hospitalization” refers to any inpatient admission (even if less than 24 hours). For chronic or long-term inpatients, inpatient admission includes transfer within the hospital to an acute/intensive care inpatient unit. Inpatient hospitalization does not include: emergency room visits; outpatient/same-day/ambulatory procedures; or admission to observation/short stay units, rehabilitation facilities, hospice facilities, nursing homes, or clinical research/Phase 1 units.

Note: The term “prolongation of existing hospitalization” refers to any extension of an inpatient hospitalization beyond the stay anticipated or required for the reason for the initial admission, as determined by the investigator or treating physician.

- a persistent or significant incapacity or substantial disruption of the ability to conduct normal life functions;

Note: A serious adverse event (SAE) specifically related to visual threat would be interpreted as any potential impairment or damage to the subject’s eyes (e.g., hemorrhage, retinal detachment, central corneal ulcer, or damage to the optic nerve).

- a congenital anomaly/birth defect; and,
- other serious (Important Medical Events) events that do not fit other outcomes, where the event may jeopardize the subject and may require medical or surgical intervention to prevent one of the outcomes listed in the SAE definition, based upon appropriate medical judgement.

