## **10.8 Safety Analysis**

Adverse events will be coded using the MedDRA dictionary.

Frequencies and percentages will be provided per treatment group of subjects with treatment-emergent adverse events (TEAEs), serious TEAEs, and TEAEs causing premature discontinuation. An adverse event is treatment-emergent if it occurs or worsens after the first dose of randomized study treatment. Furthermore, frequencies will be given of subjects with TEAEs by system organ class, by system organ class and preferred term, by system organ class, preferred term and maximal severity, by system organ class, preferred term and strongest relationship, and by system organ class, preferred term, maximal severity, and strongest relationship. Separate analyses will be performed for ocular specific and all adverse events (including systemic).

Other safety endpoints including visual acuity, slit lamp biomicroscopy, intraocular pressure (IOP), tear osmolarity and dilated fundoscopy will be summarized by treatment group and visit using descriptive statistics. Changes or shifts from baseline will also be summarized where appropriate. For assessments performed by eye, worst eye (study eye) and fellow eye will be summarized separately.

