At approximately 90-minutes post-EEC entry (and after subject assessed itching and tearing and staff assessed conjunctival redness for all time-points post first dose have been completed), a second dose (one drop in each eye) of the same randomized treatment will be administered in each eye by the qualified site staff. [REDACTED]

Visit 3 Post-EEC exit (starting at approximately t = 215 minutes):

- 1) Subject assessed ocular itching and tearing will continue [REDACTED].
- 2) Staff assessed conjunctival redness will continue to be recorded post-EEC exit [REDACTED].

Subjects will be asked to return in at least two weeks for Visit 4.

At the **Treatment EEC Session Two (Visit 4)**, all procedures performed at Visit 3 will be repeated except that each subject will be given a different treatment dependent on the treatment sequence the subject was randomized to [Reproxalap Ophthalmic Solution (0.25%) (Treatment A) or Vehicle Ophthalmic Solution (Treatment B)].

Before EEC entry, a urine pregnancy test will be administered to WOCBP.

Subjects will undergo ophthalmic examinations (Snellen VA, SLE, NCT, and a dilated fundus examination), clinical safety lab tests and vital signs will be collected to ensure safety prior to exit of the clinical trial.

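### SAP 7.2 adds a surgery or other-agent end point to the TEAE window that the protocol lacks, does not say which end date governs, and does not reopen the window at the Visit 4 dose

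*SAP*

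**What the plan says.** SAP 7.2 opens the window once: "An AE will be considered treatment emergent (TEAE) if it begins or worsens in severity after the first dose of the study drug". It closes it "through 30 days after the last dose of study drug, or the date of initiation of another investigational agent or surgical intervention". The two end points are joined by a bare conjunction, with no statement of which applies when both exist. Surgical intervention is not qualified by site, type or timing.

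The protocol defines a TEAE twice, with no such cut-off. Section 9.1.2: "A TEAE is defined as an AE that occurred during the clinical trial after the first dose of IP" (or one already present that is exacerbated after it). Section 10.8: "An adverse event is treatment-emergent if it occurs or worsens after the first dose of randomized study treatment". Collection is fixed separately in Protocol 7.6: "AEs will be collected from the time the subject signs the informed consent form through 30 days after the last dose of IP".

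On the crossover, SAP 2.1 says "Subjects will be asked to return in at least two weeks for Visit 4". SAP 7.2 assigns events to sessions by onset: "All TEAEs with start dates prior to first dose date in Visit 4 EEC Treatment Session will be classified as AEs" of the Visit 3 session.

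The SAP's summary tables of adverse events are all restricted to TEAEs. Of its three adverse event listings, one covers all AEs in the Safety Population. The other two cover serious TEAEs and TEAEs leading to discontinuation. Protocol 10.3 gives the SAP precedence over the protocol's own statistical text.

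**The concern.** A cut-off at surgery or another agent is easiest to interpret when a subject has one treatment course followed by one follow-up period. Here each subject is dosed on two days at least two weeks apart, with a different product each time. A window that opens only at the first dose, and can be closed by an event before the second, could leave the second product with no TEAE follow-up in that subject. The session rule does not prevent this, because it only sorts events that already qualify as TEAEs.

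At stake is the per-treatment count of subjects with TEAEs, including serious ones. The affected product would depend on the sequence, so no direction of bias can be stated in advance. The clause also runs against the cautious conventions elsewhere in the SAP. A missing relationship is counted as related, missing severity as severe, and ambiguous partial onset dates are set to the day of treatment (SAP 4.5 and 7.2).

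**Working it through.** The documents give no figure on this point, so there is none to reproduce. The check compares the possible readings and counts days.

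**Inputs**
- Window start: first dose, at Visit 3, taken as day 0 (SAP 7.2).
- Gap between treatment sessions: at least 14 days (SAP 2.1). Assumed to be exactly 14.
- Tail: 30 days after the last dose (SAP 7.2), the same as the end of AE collection (Protocol 7.6 and 9).

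**Full window:** 14 + 30 = 44 days, of which 30 follow the Visit 4 dose.

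**Three readings of the clause**
1. Earlier date, applied throughout.
2. Earlier date, but only as a cap on the tail after the last dose.
3. Later date.

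**Case A: surgery on day d between the sessions (0 < d < 14), subject still dosed at Visit 4**

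| Reading | Days lost | Days covered after the Visit 4 dose |
|---|---|---|
| 1. Earlier date throughout | 44 − d | 0 of 30 |
| 2. Cap on the final tail only | 0 | 30 of 30 |
| 3. Later date | 0 | 30 of 30 |
| Protocol definitions | 0 | 30 of 30 |

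Under reading 1 the loss is more than 30 and fewer than 44 of the 44 days, so above 30/44 = 68%. For illustration, d = 7 leaves 7/44 = 16% of the window. A longer gap changes the total, but the figure of 0 of 30 after Visit 4 stays the same.

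**Case B: surgery s days after the Visit 4 dose (0 < s < 30)**

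Readings 1 and 2 both lose 30 − s of the 30 days. Reading 3 and the protocol definitions lose none.

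**Does the later-date reading make sense of the clause?** Hardly. Surgery inside the 44 days would leave the end at day 44, exactly as if the clause were absent. Surgery after day 44 would extend the window into a period in which no new AEs are collected. At most it could pick up worsening of an AE still being followed under Protocol 9.1.6. The clause has real effect only if it shortens the window, as in readings 1 and 2. A programmer is therefore likely to implement a truncation, and the text does not tell that programmer to wait for the final dose. Where the protocol wants the later of two dates it says so, as for pregnancy reporting in 9.1.8.

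**What is excluded under truncation.** New or worsening events after the cut-off leave every TEAE table and the serious-TEAE and discontinuation-TEAE listings. They stay in the All AEs listing.

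**The case against.** The strongest reply is that the SAP does not say the earlier date governs. The second limb can be read as capping the 30-day tail after the last dose, and then a procedure between sessions removes nothing after Visit 4. That stands: the loss in Case A follows from one reading and is not a certainty. It does not help Case B, and the open choice between readings is itself a defect in a plan meant to be final before database lock.

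Other parts of the reply also stand:
- Protocol 6.7 bars concurrent enrolment in another drug or device trial, so the other-agent limb should not arise between sessions.
- Protocol 6.7.1 refers to the exclusion criteria for prohibited procedures, and several of those are blacked out. Eligibility is reviewed again at Visit 4 (Protocol 8.5), and subjects may be discontinued for AEs, protocol violations or medical reasons (5.2). Surgery is not a listed reason, so the scenario is possible, but how far it is limited cannot be seen.
- Whether a small procedure counts as surgical intervention is undefined.
- The SAP reports subject counts per treatment, not a within-subject safety comparison. The two products have unequal follow-up in any case, about 14 days against 30.

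Two stronger inferences are tempting and should not be drawn. A reader might infer that a subject's later events vanish. They do not: AEs are collected to 30 days after the last dose regardless, SAEs are reported over the same period regardless of causality (Protocol 9.1.5), and all are listed. A reader might also infer that the event needing surgery is lost, since Protocol 9.1.3 refers to events that "may require medical or surgical intervention to prevent one of the outcomes listed in the SAE definition". That wording belongs to the important-medical-event category and does not make every procedure a sign of seriousness. Under Protocol 9.1.1 the condition leading to a procedure is the AE. If it began after the first dose and before the surgery, it still counts as a TEAE. Only new or worsening events after the surgery are exposed.

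**Conclusion.** The point holds as an ambiguity and a conflict with the protocol, one that can misclassify events in the formal safety outputs. The added end point is absent from Protocol 9.1.2 and 10.8, its governing date is unstated, and the window does not reopen at the Visit 4 dose. Applied as the earlier date throughout, it leaves 0 of 30 days of TEAE coverage for the second product after surgery between sessions. Under either truncating reading it loses 30 − s days after surgery on day s following Visit 4.

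This rests on three assumptions: that the clause is programmed as a truncation, that a subject with surgery between sessions can still be dosed at Visit 4 (needed for Case A only), and a 14-day gap (which affects only the 44-day total). The documents give no procedure rate, so the number of subjects cannot be computed. Over a gap of about two weeks and a 30-day tail it is likely to be few if any. Severity: minor.

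**What to change.** In SAP 7.2, delete the second end point, so that a TEAE is any AE starting or worsening in severity after the first dose through 30 days after the last dose. That removes the cut-off which Protocol 9.1.2 and 10.8 lack and fits the collection period in Protocol 7.6. In the AE listing, flag events that begin or worsen after a procedure or another investigational agent, so that a reader can judge confounding.

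If the sponsor prefers to keep a cut-off, the minimum is to state that it cannot take effect before the final dose. It should also say which date governs and define surgical intervention. This repairs Case A but leaves the truncation in Case B.

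The cost of deletion is one clause of SAP wording and one listing flag, which needs only the dates that the present clause would need anyway. The downside is that a few events caused by the procedure itself may be counted as TEAEs, and the flag identifies them. Efficacy analyses and data collection are unaffected.

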#### **9.1.1.3 Assessment of Causality and Severity**

For each AE recorded, the investigator will make an assessment of causality and severity as follows:

1. Relationship to IP: The investigator must assess whether they consider an AE to be drug-related. In assessing this relationship, the investigator must use information about the drug as outlined in the Investigator's Brochure, the subject's pre-existent medical conditions/concurrent medication, and chronology of the event relative to drug administration. The following definitions will be used:
  - Definitely Related
  - Probably Related
  - Possibly Related
  - Unlikely to be related
  - Not Related
2. Event Severity: The investigator will be asked to use their medical judgment to assess the severity of the AE.

The following are guidelines to be used by the investigator to judge the event severity of an AE:

3. **Expectedness:** The expectedness of an AE should be determined based on existing safety information about the IP using the following explanations:

- *Unexpected*: an AE that is not listed in the IB or is not listed at the specificity or severity that has been observed.
- *Expected*: an AE that is listed in the IB at the specificity and severity that has been observed.
- *Not applicable*: an AE unrelated to the IP.

AE events that are mentioned in the IB as occurring with a class of products or as anticipated from the pharmacological/mechanical (or other) properties of the product, but are not specifically mentioned as occurring with the particular product under investigation, are to be considered unexpected.

The investigator should initially classify the expectedness of an AE, but the final classification is subject to the determination of the Sponsor's Medical Monitor.

4. Duration: Start and end dates and times, or if continuing.
5. Frequency: whether the event is a single episode, recurrent or continuous.
6. Action taken.
7. Whether it constitutes a SAE, per definition below.
8. Outcome: resolved, resolved with sequelae, continuing, death, or unknown (only for subjects that are lost to follow-up).

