At all EEC sessions, assessments of ophthalmic evaluations will be collected [REDACTED]. [REDACTED]. In the event of an [REDACTED] failure, paper diary cards will be used as a back-up to collect symptom scores. For subject-reported symptoms of ocular itching, a standard 9 point (i.e., 0-4 with 0.5 unit increments) scale will be employed. For staff-assessed grading of conjunctival redness, a standard 9-point (i.e., 0-4 with 0.5 unit increments) will be employed. [REDACTED]

[REDACTED]

At the **EEC Screening Visit (Visit 2)**, qualified site staff will update concomitant medications and collect AEs, as applicable and perform tests for vital signs. A urine pregnancy test will be administered to WOCBP. Fundus exam, Snellen VA, SLE, subject rating of symptoms, and staff grading of conjunctival redness will be performed to ensure the anterior segment of the eye is healthy. [REDACTED]

Visit 2 Pre-EEC entry (Baseline):

- 1) Subject assessment for ocular itching and tearing will be recorded [REDACTED], and [REDACTED]
- 2) Staff-assessed conjunctival redness will be recorded [REDACTED].

Visit 2 Post-EEC entry:

- 1) Subject assessment for ocular itching and tearing will occur [REDACTED].
- 2) Staff-assessed conjunctival redness will be recorded [REDACTED].

[REDACTED]

At the **Randomization/Treatment EEC Session One (Visit 3)**, qualified site staff will update concomitant medications, collect AEs, as applicable and collect vital signs. A urine pregnancy test will be administered to WOCBP. Ophthalmic evaluations will be conducted (Fundus exam, Snellen VA, NCT SLE, subject rating of symptoms, and staff grading of conjunctival redness). [REDACTED]

Subjects will be randomized to receive a first dose of either Reproxalap Ophthalmic Solution (0.25%) (Treatment A) or Vehicle Ophthalmic Solution (Treatment B). Qualified site staff will instill one drop of the randomized treatment into each eye at approximately time zero [REDACTED] prior to entry to the EEC after all the pre-EEC assessments are done.

Visit 3 Pre-EEC entry (Baseline):

- 1) Subject assessment for ocular itching and tearing will be recorded [REDACTED] and [REDACTED]
- 2) Staff-assessed conjunctival redness will be recorded [REDACTED].

Visit 3 Post-EEC entry:

- 1) Subject assessment for ocular itching and tearing will occur [REDACTED].
- 2) Staff-assessed conjunctival redness will be recorded [REDACTED].

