4.5 Handling Partial Dates for Adverse Events

When determining the treatment emergent AE, partial dates will be handled as follows.

- If the day of the month is missing, the onset day will be set to the first day of the month unless it is the same month and year as first dose date. In this case, the onset date will be assumed to be the first date of treatment.
- If the onset day and month are both missing, the day and month will be assumed to be January 1, unless the event occurred in the same year as the study treatment. In this case, the event onset will be coded to the day of treatment to conservatively report the event as treatment-emergent.
- A missing onset date will be coded as the day of treatment. If the resulting onset date is after a reported date of resolution, the onset date will be set equal to the date of resolution.
- Imputation of partial dates is used only to determine whether an event is treatment-emergent; data listings will present the partial date as recorded in the eCRF.

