6.1 General Statistical Procedures

Frequency distributions for categorical variables will be provided as number of patients in the category and the percentages of the total number of patients in the given population as noted. Percentages will be reported to one decimal place.

The descriptive statistics for continuous variables will be number of subjects (n), mean, standard deviation (SD), median, minimum and maximum. Mean and median will be reported to 1 more decimal place than the raw data, while the SD will be reported to 2 more decimal places than the raw data. Minimum and maximum will be reported the same as the original data.

All statistical tests will be two-sided with a significance level of 0.05 ($\alpha = 0.05$) unless otherwise specified. Confidence interval (CI) for differences between treatment will be two-sided at 95% confidence interval.

P-value will be rounded to at most 3 decimal places and will be reported as < 0.001 if it is smaller than 0.001.

Unless otherwise specified, subjects' characteristics at baseline will be summarized by treatment sequences (Reproxalap 0.25%/Vehicle, Vehicle/Reproxalap 0.25%). Safety and efficacy will be summarized by treatment (Reproxalap 0.25%, Vehicle) where appropriate.

In general, all listings will be ordered by subject number and visit for available data unless otherwise specified in the text.

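### SAP 7.2 assigns adverse events to a session by start date alone, so an event on the Visit 4 date before dosing is not placed in Visit 3; SAP 6.2 also expresses screen failures as a percentage of subjects randomized

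*SAP*

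**What the plan says.** **Session rule.** SAP 7.2 reports TEAEs by treatment ("An overall summary for number of subjects with events in each treatment will be provided including" a list of counts) and allocates them to sessions with one sentence: "All TEAEs with start dates prior to first dose date in Visit 4 EEC Treatment Session will be classified as AEs occurred in Visit 3". The comparison is between two dates. No time of day enters it, and nothing is written for a start date equal to the Visit 4 date.

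**What is collected.** Protocol 9.1.1.3 requires, for each adverse event, "Start and end dates and times, or if continuing".

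**Order of events on a treatment day.** In SAP 2.1 the first drop at Visit 3 is given "prior to entry to the EEC after all the pre-EEC assessments are done". For Visit 4 the same section says that "all procedures performed at Visit 3 will be repeated except that each subject will be given a different treatment". Protocol 7.10.2 schedules the slit lamp examination before as well as after chamber entry at Visits 2 to 4, and protocol 8.5 collects adverse events at Visit 4.

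**Incomplete dates.** SAP 4.5 says "A missing onset date will be coded as the day of treatment", without saying which of the two treatment days is meant when no date is recorded. It also says "Imputation of partial dates is used only to determine whether an event is treatment-emergent".

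**Percentages.** SAP 6.1 gives the general rule: counts and "the percentages of the total number of patients in the given population as noted". SAP 7.2 names no denominator of its own. SAP 6.2 names two. Its first table, for the Enrolled Population by sequence and overall, uses the number randomized. Its discontinuation table, by treatment, uses the number in the Safety Population. The first row of the first table is screen failures.

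**The concern.** In a two-period crossover, the by-treatment safety table is only as good as the rule that attaches each event to a period. Under the written rule, an event noticed on the morning of Visit 4, before any drop of the second product, is not attached to the first session. The only other session is the second, so the event would be counted against a product that cannot have caused it. The direction depends on sequence. In AB such an event moves from reproxalap to vehicle, and in BA from vehicle to reproxalap.

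The disposition point is of a different kind. A screen failure is by definition a subject who was not randomized (SAP 2.3.1), so a percentage of subjects randomized has a numerator that is not part of its denominator.

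**Working it through.** The documents state no figure on either point, so there is nothing to reproduce first.

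**1. The session rule applied to three onsets.** Assume, for illustration, that the first Visit 4 dose is at 09:00.

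| Onset | Start date before Visit 4 date? | Session under SAP 7.2 | Session by date and time |
|---|---|---|---|
| Evening before Visit 4 | Yes | Visit 3 | Visit 3 |
| Visit 4 date, 07:30, before the drop | No | Not Visit 3 | Visit 3 |
| Visit 4 date, 10:00, after the drop | No | Not Visit 3 | Visit 4 |

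Only the middle row changes. Such an event is treatment-emergent, because it begins after the first dose at Visit 3 and before the end of follow-up. The pre-dose window exists, because examinations and adverse event collection take place on that day and the drop follows all the pre-chamber assessments. The documents give no event rate for this window, so the number of such events cannot be computed.

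**2. Incomplete dates.** The imputed date in SAP 4.5 may be used only to decide treatment emergence. It therefore does not supply a session, and SAP 7.2 has no fallback where the recorded date leaves the session open.

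**3. Screen failures.** Inputs: 670 screened and 126 randomized (SAP 2.2).

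- Screen failures: 670 − 126 = 544.
- Under the stated base: 544/126 = 4.317, or 432%.
- Over those screened: 544/670 = 81.2%; subjects randomized: 126/670 = 18.8%.

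The last line assumes that the 670 are the Enrolled Population. SAP 5.1 defines that population by signed consent, while SAP 2.2 speaks of 670 screened in the chamber, so more may have consented. In that case both screen-failure percentages would be higher.

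**4. Why the by-treatment base is worth confirming.** Suppose all 126 are dosed, 100 are dosed twice, and the remaining 26 are dosed only at Visit 3. The 26 is the gap between two planning numbers, and its split between sequences is assumed. With *a* lost after reproxalap and *b* lost after vehicle, 126 − *b* received reproxalap and 126 − *a* received vehicle.

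- Even split (13 and 13): 113 received each product. Ten subjects with an event are 10/126 = 7.9% on a pooled base and 10/113 = 8.8% on a received-treatment base. The relative understatement is 1 − 113/126 = 10.3% for both, so their ratio is unchanged.
- Extreme split (all 26 from one sequence): 100 received one product and 126 the other. Ten subjects are 10/100 = 10.0% against 10/126 = 7.9%.

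These figures apply only if the pooled base is meant, which the documents do not establish.

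**The case against.** The strongest reply on the session rule is that a programmer would naturally use the recorded time, that few events will start in the hours before the Visit 4 drop, and that adverse event listings are planned, so a misplaced event could be found. That bears on size and stands. It does not change the text, which compares dates, and a listing does not correct a table.

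On disposition, a reader might infer that SAP 6.2 leaves its denominators unstated or hides losses by sequence. The documents do not support this. Both denominators are given, and the by-sequence table has a row for subjects who finished only the first session. With 13 such subjects in a sequence of 63, that row would show 13/63 = 20.6%. What remains open is which treatment a withdrawal between sessions is counted under, and whether the by-treatment base is the whole Safety Population or only those given that product.

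A reader might also infer that adverse event rates will be diluted by a pooled Safety Population. SAP 6.1 with SAP 5.2 can be read that way, but a column N per treatment fits the wording too. The body of SAP Table 2, which assigns populations to tables, is not available in the text reviewed. This supports a request for confirmation and nothing stronger.

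On incomplete dates, SAP 4.5 does name the first date of treatment when only the day is missing and the month is that of the first dose. Since it confines imputation to treatment emergence, a gap remains, but a small one. It might also seem natural to count events of unknown session under reproxalap as the conservative choice. The conservatism in SAP 4.5 concerns whether an event is treatment-emergent, not which product carries it, so that default does not follow from the plan.

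The screen-failure base may be called a wording slip that would mislead nobody. It is still a stated rule that yields an impossible percentage.

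**Conclusion.** Two stated rules need correction. The date-only session rule in SAP 7.2 does not place a same-day pre-dose event at Visit 4 in Visit 3, and by implication counts it under a product not yet given. Its numerical effect cannot be computed and is probably small. The base in SAP 6.2 gives about 432% for screen failures at planned numbers, against 81.2% if the 670 screened are the Enrolled Population.

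The by-treatment denominators and the attribution of between-session withdrawals are matters to confirm, not demonstrated errors. Only descriptive safety and disposition tables are touched, and no efficacy analysis is affected. Severity: minor.

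**What to change.** - **SAP 7.2:** assign each TEAE to a session by comparing its start date and time with the time of the first Visit 4 dose. Footnote the number of events whose session remains unknown because the time is missing or the date is partial.
- **SAP 6.2:** use the Enrolled Population as denominator for screen failures and for subjects randomized, and show both in the all-subjects column only. Keep subjects randomized as the base for the other rows.
- **To confirm, in 6.2 and 7.2:** that by-treatment adverse event and discontinuation percentages use Safety Population subjects who received that treatment, and under which treatment a withdrawal between sessions is counted.

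The cost is a few sentences and the column Ns in the table shells. The protocol already requires start times, so no new data are needed.
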